### **8.2 Other Toxicity**

The occurrence of **treatment-related** Grade 4 adverse events in any organ system will prompt discontinuance of protocol therapy while appropriate physical examination, laboratory, and imaging assessments are undertaken per each institution's standard of care. Protocol treatment will not be resumed in the absence of recovery from adverse events of this magnitude. Once recovery to  $\leq$  grade 2 has occurred, treatment may continue at the discretion of the treating physician.

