## **8.0 Treatment Modifications**

8.1 Hepatic Toxicity: Subjects will be evaluated for symptoms and signs of RILD or other toxicity. It is expected that a proportion of subjects will have transient elevation of liver enzymes during treatment. Repeat of all Grade 4 LFTs is required within 5-10 days following the first abnormal lab value to determine if the Grade 4 levels are transient (defined here as <10 days) or persistent. Subjects exhibiting hepatic toxicity  $\geq$  5-20x baseline LFT's will be evaluated with radiological imaging procedures to assess whether change in LFTs are due to tumor progression or treatment toxicity. Subjects whose progressive liver function abnormalities while under treatment are deemed due to tumor progression will stop all protocol treatment and will be managed and followed per physician standard of care. Subjects with treatment induced hepatic toxicity of greater than 20x baseline elevation will not receive further protocol treatment unless and until liver function tests have returned to less than 5x subjects baseline value. Subjects will be evaluated for symptoms and signs of RILD or other toxicity per the schedule described in the protocol or more frequently depending on the clinical judgment of the treating team. If recovery of hepatic function requires an interruption of treatment of more than 30 days, patients will be withdrawn from the study.

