### **10.3 Possible long term toxicities after SBRT:**

- Gastric or Bowel injury (ulceration, bleeding, perforation, fistula formation, or obstruction)
- Biliary obstruction due to inflammation or sclerosis
- Liver abscess
- Hepatic subcapsular injury
- Decreased renal function.
- Rib fracture
- Myositis
- Radiation-induced liver disease (RILD) including potentially fatal liver injury.
- In subjects who have Grade 4 elevation of liver enzymes levels and/or in subjects with early nonspecific signs or symptoms of liver injury, close follow-up is recommended with repeat blood work. If no tumor progression is documented in these subjects, liver injury will be presumed to be treatment related.

Only grade  $\geq 2$  toxicities will be considered in the statistical analysis. The following toxicities will require subjects to be removed from protocol treatment if the protocol treatment has not yet been completed. Patients will be followed per physician standard of care.

- Grade  $\geq 4$  hepatic toxicity for changes in AST, ALT, alkaline phosphatase, or platelet counts attributed to treatment and not attributable to disease progression. Transient grade 4 (less than 10 days) hepatic toxicities are acceptable.
- Grade  $\geq 4$  Upper GI bleeding (**attributed to treatment**, and not attributable to disease progression).
- Death due to any cause.

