## **12.0 Criteria for Discontinuation of Protocol Treatment**

### **12.1 Off-Treatment Conditions**

- Unacceptable toxicity as defined in section 10.
- Therapy may be discontinued prematurely at any time by subject request without prejudice to subsequent care.
- Subjects may be removed from the treatment at any time per investigator discretion.

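### A treatment-related grade 4 upper GI bleed that recovers may go on to further treatment under section 8.2 but must be removed under section 10.3, and no precedence is stated

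*Combined protocol and SAP*

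**What the plan says.** Section 8.2 (Other Toxicity) says that treatment-related "Grade 4 adverse events in any organ system will prompt discontinuance of protocol therapy" while the patient is assessed. Without recovery, treatment does not resume. After recovery to grade 2 or lower, "treatment may continue at the discretion of the treating physician". Section 8.3 lists exceptions to stopping (low albumin, low lymphocytes, brief hyperglycemia in type II diabetics). None concerns bleeding.

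Section 10.3 states: "The following toxicities will require subjects to be removed from protocol treatment if the protocol treatment has not yet been completed". Its list includes grade 4 or higher "Upper GI bleeding" that is attributed to treatment and not to progression. It also includes grade 4 or higher "hepatic toxicity for changes in AST, ALT, alkaline phosphatase, or platelet counts attributed to treatment and not attributable to disease progression". The one exception is hepatic: "Transient grade 4 (less than 10 days) hepatic toxicities are acceptable". Section 12.1 makes "Unacceptable toxicity as defined in section 10" an off-treatment condition.

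Section 8.1 (Hepatic Toxicity) has its own rule. Patients with treatment-induced elevation above 20 times baseline "will not receive further protocol treatment unless and until liver function tests have returned to less than 5x subjects baseline value". Withdrawal from the study follows only if recovery needs an interruption of more than 30 days. Section 8.1 also has grade 4 liver tests repeated so that they can be called transient (under 10 days) or persistent, but it names no consequence for persistent ones.

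Sections 8.1 to 8.3 do not mention 10.3.

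**The concern.** Section 8 is titled Treatment Modifications and carries its own exceptions list, so it reads as complete. A physician deciding whether to re-treat after a serious toxicity would look there first. For a bleed that has settled, that physician finds an express permission to continue. Section 10.3 withholds that permission, but its removal list follows a set of long-term SBRT toxicities, where a TACE team might not look.

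The stake is patient safety and consistency between sites. In a multicenter trial, two sites could handle the same recovered patient in opposite ways, each citing the protocol. A mandatory stopping rule should not depend on the physician declining a permission that the protocol grants elsewhere.

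**Working it through.** No statistical calculation applies. The check sets the rules side by side for the same patient.

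**1. Do the two rules cover the same event?** Section 8.2 applies to treatment-related grade 4 events in every organ system. Section 10.3 applies to upper GI bleeding of grade 4 or higher attributed to treatment. A treatment-related grade 4 upper GI bleed falls under both. A fatal bleed cannot recover, so the conflict concerns grade 4 only.

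**2. What does each rule require once the bleed has recovered to grade 2 or lower and treatment is not complete?**

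| Source | Disposition |
|---|---|
| 8.2 | Further protocol treatment allowed, at the physician's discretion |
| 8.3 | Silent on bleeding |
| 10.3 | Removal from protocol treatment; no recovery clause; the transient exception is hepatic only |
| 12.1 | Off treatment, by pointing to section 10 |

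One event has two outcomes.

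**3. Is precedence stated?** No. Sections 8.1 to 8.3 do not defer to 10.3, and 12.1 does not say that section 10 overrides section 8.

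**4. How much treatment is at stake?** Section 5.4 allows at most three TACE procedures as initial therapy, about 4-6 weeks apart, so 3 − 1 = 2 could follow a bleed after the first. Section 4.4.3.1 sets five SBRT fractions within 15 days, so 5 − 1 = 4 could follow a bleed after the first fraction. These are ceilings. Four fractions would need bleed, recovery and the rest of the course all inside 15 days, which leaves little room. A repeat TACE is given only if stasis was not achieved, and at the interventional radiology team's discretion.

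**5. Does 8.1 conflict with 10.3 in the same way?** Only approximately.

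| | 8.1 | 10.3 (AST, ALT, alkaline phosphatase) |
|---|---|---|
| Scale | Multiples of the patient's baseline (20x, 5x) | CTCAE grade 4 or higher |
| Clock | Length of the interruption until hepatic function recovers | Days at grade 4 |
| Limit | More than 30 days | 10 days or more |
| Consequence | Withdrawal from the study | Removal from protocol treatment |

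A patient above 20 times baseline whose grade 4 tests last 10 days or more, and who then falls below 5 times baseline within the 30-day limit, may resume under 8.1 but is removed under 10.3. By contrast, a patient at grade 4 for 8 days who needs 25 days to fall below 5 times baseline may resume under both. The documents do not map multiples of baseline to grades, so the tension is real but its extent cannot be fixed.

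**The case against.** The strongest reply is that the text already resolves the point. Section 10.3 is specific and mandatory, 8.2 is general and permissive, 12.1 points to section 10, and a physician who stops complies with both. That is very probably the intent. It does not remove the defect: a physician who uses the permission in 8.2 follows that section and breaches 10.3, with no statement of which prevails.

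A second reply is that a safeguard exists. A grade 4 GI bleed would very likely be a serious adverse event under 12.4.1. It would be reported within one working day (12.4.4, 18.2) and reviewed in real time (18.2). With TACE procedures weeks apart, a misreading could be caught. This limits the harm, but the people reviewing the event would face the same two rules.

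A third reply is that the removal list sits under a heading about SBRT toxicities. If it applies to SBRT alone, the TACE conflict disappears and only the short SBRT window is left. The list speaks of subjects generally, which favors both arms, but the point is open and the repeat-TACE risk depends on it.

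A fourth reply is that 8.1 and 10.3 complement each other: 8.1 classifies grade 4 tests at 10 days and 10.3 supplies the consequence. That is a fair reading. It still leaves the reader of 8.1 with a resumption rule and no pointer to that consequence.

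**Conclusion.** The point holds as a contradiction between two safety rules. The clear instance is a treatment-related grade 4 upper GI bleed that recovers before protocol treatment is complete. The liver-test rules in 8.1 and 10.3 are a secondary, inexact tension. The conclusion on bleeding rests only on the wording; its reach into the TACE arm assumes that the removal list covers both arms. The documents give no frequency for these events, so the number of patients affected cannot be stated. The correction should be made, but it is small and leaves power, sample size and the primary analysis unchanged.

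Three stronger readings are tempting, and the documents do not support them:

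- A reader might set the 10-day and 30-day limits against each other and infer a fixed window of conflict for liver tests. The limits count different things, and a shared start would not make their end points the same.
- A reader might apply the 10-day limit to bleeding and work out a latest onset day before the next TACE. That limit belongs to hepatic toxicity only; bleeding has no duration threshold in 10.3.
- A reader might count platelets as a further conflict. Section 10.3 places platelet counts under hepatic toxicity, while 8.2 is headed as covering other toxicity. Whether 8.2 reaches them is a matter of reading, and no conflict is shown.

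**What to change.** - Add to 8.1 and 8.2: *except for toxicities listed in 10.3, for which subjects are removed from protocol treatment*.
- State in 8.1 that persistent (10 days or more) grade 4 liver tests attributed to treatment are handled under 10.3.
- Move the removal list out from under the SBRT toxicity heading into its own section, stated to apply to both arms.

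Adding a recovery clause to 10.3 would also end the contradiction, but it would loosen a mandatory stopping rule that 12.1 relies on. Deferring to 10.3 is the safer choice.

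The cost is a wording amendment. A few recovered patients lose the option of further protocol treatment. Section 10.3 already requires that, and provides for their follow-up under the physician's standard of care.

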### **8.3 Exceptions that will not require discontinuation of therapy**

- Grade 3 or 4 asymptomatic hypo-albuminemia or decreased lymphocytes.
- Transient (< 48 hours) asymptomatic grade 3 fasting hyperglycemia in type II diabetics.

## **9.0 SBRT Dose Adjustment**

There will be no dose adjustments for SBRT treatment.

## **10.0 Toxicity Considerations**

The criterion used for the grading of toxicities is the Common Terminology Criteria for Adverse Events (CTCAE) Version 5.0.

### **10.1 Expected Toxicities after TACE:**

- Abdominal pain
- Nausea
- Vomiting
- Fatigue

### **10.2 Expected Acute Toxicities after SBRT:**

- Fatigue
- Weight loss
- Nausea, vomiting, or anorexia.
- Abdominal discomfort.
- Skin irritation
- Increased frequency of bowel movements or change in stool consistency

### **10.3 Possible long term toxicities after SBRT:**

- Gastric or Bowel injury (ulceration, bleeding, perforation, fistula formation, or obstruction)
- Biliary obstruction due to inflammation or sclerosis
- Liver abscess
- Hepatic subcapsular injury
- Decreased renal function.
- Rib fracture
- Myositis
- Radiation-induced liver disease (RILD) including potentially fatal liver injury.
- In subjects who have Grade 4 elevation of liver enzymes levels and/or in subjects with early nonspecific signs or symptoms of liver injury, close follow-up is recommended with repeat blood work. If no tumor progression is documented in these subjects, liver injury will be presumed to be treatment related.

Only grade  $\geq 2$  toxicities will be considered in the statistical analysis. The following toxicities will require subjects to be removed from protocol treatment if the protocol treatment has not yet been completed. Patients will be followed per physician standard of care.

- Grade  $\geq 4$  hepatic toxicity for changes in AST, ALT, alkaline phosphatase, or platelet counts attributed to treatment and not attributable to disease progression. Transient grade 4 (less than 10 days) hepatic toxicities are acceptable.
- Grade  $\geq 4$  Upper GI bleeding (**attributed to treatment**, and not attributable to disease progression).
- Death due to any cause.

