### **12.3 Adverse Event Guidelines**

#### **12.3.1 Adverse Event definitions**

- An Adverse Event is any untoward medical event that occurs in a subject who has received an investigational treatment, and does not necessarily have a causal relationship with the investigational treatment. An AE can therefore be any unfavorable and unintended sign (including abnormal laboratory finding), symptom, or disease temporally associated with the use of an investigational treatment, whether or not related to the treatment.
- Pre-existing diseases or symptoms or abnormal laboratory values present upon recruitment are not considered an AE even when observed during the further course of the study. However, every worsening of a pre-existing condition is considered an adverse event.
- All AEs  $\geq$  grade 3 will be collected and attributed either as possibly, probably or definitely related to protocol treatment or not related to protocol treatment. Additional AE's collected are, any grade  $\geq 2$  abdominal pain, nausea, vomiting, and fatigue. The NCI Common Terminology Criteria for Adverse Events Version 5.0 (CTCAE) will be utilized to grade AE's for AE reporting.

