#### 12.4 SAE Guidelines

12.4.1 A serious adverse event (SAE) shall be defined as an adverse event which fulfills one or more of the following criteria:

- Results in death
- Is immediately life-threatening
- Requires in-subject hospitalization or prolongation of existing hospitalization
- Results in persistent or significant disability or incapacity
- Is an important medical event that may jeopardize the subject or may require medical intervention to prevent one of the outcomes listed above
- **Any events or hospitalizations that are unequivocally due to progression of disease should not be reported as an SAE.**
- The causality of SAEs (i.e., their relationship to study treatment) will be assessed by the site investigators and will be labeled as either related to treatment, or not related to treatment.

12.4.2 Only adverse events deemed serious AND related will be reported to the IRB within 10 days of awareness of the event, or per institutional Policy. All other events will be noted in the subjects' medical record.

12.4.3 The following types of hospitalizations do not constitute SAEs:

- Hospitalization or Emergency room visits secondary to expected cancer morbidity.
- Admission for palliative care or pain management.
- Planned hospitalizations for surgical procedures either related or unrelated to the subject's cancer.

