### 17.1 Primary endpoint

The primary analysis of the primary endpoint of time from randomization to residual or recurrent disease will be based upon the Kaplan-Meier estimates of time to event for the two groups where the two groups are compared using the log-rank test. Patients will be censored at time of transplantation or two years, whichever comes first. The primary analysis will treat patient death as residual or recurrent disease (effectively the compound endpoint of residual or recurrent disease or death). During the time frame of two years mortality should be low, but treatment of death as residual or recurrent disease is conservative. Secondary analyses using the Cox regression model will explore predictors of recurrence beyond group assignment, and also explore interactions between treatment and these other factors. We will also explore sex and treatment center differences. Secondary analyses will also censor for deaths unrelated to treatment. Statistical tests will be made at the two-sided 5% level.

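### The presumption that liver injury without progression is treatment related is printed only under the SBRT toxicity heading; its scope is unclear, so equal injuries may be attributed differently by arm

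*Combined protocol and SAP*

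**What the plan says.** All references are to the combined protocol and SAP.

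- **The rule.** Section 10.3 is headed "Possible long term toxicities after SBRT". Its last bullet concerns a group defined as follows: "In subjects who have Grade 4 elevation of liver enzymes levels and/or in subjects with early nonspecific signs or symptoms of liver injury". It recommends close follow-up with repeat blood work, then adds: "If no tumor progression is documented in these subjects, liver injury will be presumed to be treatment related".
- **TACE.** Section 10.1, "Expected Toxicities after TACE", lists abdominal pain, nausea, vomiting and fatigue. It has no liver item and no presumption.
- **Work-up in 8.1.** This section is not limited to one arm. It sends marked enzyme rises to imaging to separate tumor progression from treatment toxicity, and sets no default attribution.
- **Labels.** Under 12.3.1, events of grade 3 or higher are "attributed either as possibly, probably or definitely related to protocol treatment", or else not related. Under 12.4.1, site investigators decide whether an SAE is related.
- **Uses of the label.** Section 12.4.2: "Only adverse events deemed serious AND related will be reported to the IRB", within 10 days or per institutional policy. Section 17.1: "Secondary analyses will also censor for deaths unrelated to treatment".
- **Context.** Section 15.0 describes the trial as non-blinded. In 17.1 the primary analysis counts every death as an event, and two-year mortality is expected to be low.

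**The concern.** A presumption takes a decision away from the person who would otherwise make it. If sites read this one as belonging to the heading it stands under, liver injury without progression is called related after SBRT by default, but only on the investigator's opinion after TACE. That opinion has room to differ. Section C notes that people with HCC typically also have cirrhosis, so the underlying disease is always an available explanation. It also reports liver abscesses after drug-eluting-bead TACE, one of them fatal, so liver injury in that arm is not hypothetical. The investigators know the arm.

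Three things depend on the label: the recorded relatedness of events of grade 3 or higher, which serious events go to the IRB, and which deaths are censored in the secondary analysis of the primary endpoint. Section 17.1 does not say how a death is judged unrelated. Attribution made during the trial under an unclear rule is hard to repair afterwards.

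**Working it through.** **1. Scope of the rule, from the text.** Two readings are open.

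- *SBRT only:* the sentence sits under an SBRT heading, directly after the bullet on radiation-induced liver disease, and 10.1 has nothing like it.
- *Both arms:* the bullet speaks only of subjects. The same heading also carries rules that are plainly general, such as the toxicity grade that enters the statistical analysis, and this: "The following toxicities will require subjects to be removed from protocol treatment if the protocol treatment has not yet been completed". Section 12.1 then applies section 10's definition of unacceptable toxicity to all subjects.

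The text does not settle which is meant.

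**2. Which analyses use relatedness.** The primary log-rank test does not, because all deaths are events. The toxicity and adverse-event comparisons in 17.2.3 and the adverse-events paragraph do not either; they go by count, body system and severity. Only the secondary analysis in 17.1 that censors unrelated deaths does.

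**3. The plan's own event count (section 16.0, Table 7).** Inputs: HR 0.6, two-sided 5%, 1:1 allocation. Schoenfeld's formula is D = 4(z_α/2 + z_power)² / (ln HR)².

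- 80% power: 4 × (1.960 + 0.842)² / (ln 0.6)² = 120.3; plan 120.
- 90% power: 4 × (1.960 + 1.282)² / (ln 0.6)² = 161.1; plan 161.

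The plan's counts are reproduced.

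**4. Split of 120 events by arm.** Inputs from Table 7: medians 134 and 223.3 days (134/0.6), 365 days of uniform accrual, 730 days in total, 15% yearly dropout. With λ = ln 2/median and γ = −ln(0.85)/365, the event probability is λ/(λ+γ) × [1 − mean of exp(−(λ+γ)f)], with f uniform on 365 to 730 days. This gives 0.870 for TACE and 0.740 for SBRT. Scaled to 120 events, the split is 64.8 TACE and 55.2 SBRT. This is a continuous-time approximation; the plan's discrete three-monthly model was not replicated.

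**5. Effect of unequal counting.** Let k be the number of deaths per arm after liver injury without progression. The documents give no rate, so k is an assumption. A death ends follow-up whether it is counted or censored, so person-time cancels between counting rules.

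- Counted in both arms: HR = 0.6 × [(55.2+k)/55.2] × [64.8/(64.8+k)]
- Counted under SBRT, censored under TACE: HR = 0.6 × (55.2+k)/55.2
- The same unequal counting with no true effect (60 events per arm): HR = (60+k)/60

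| k per arm | Both counted | SBRT only | SBRT only, no true effect |
|---|---|---|---|
| 0 | 0.600 | 0.600 | 1.000 |
| 1 | 0.602 | 0.611 | 1.017 |
| 2 | 0.603 | 0.622 | 1.033 |
| 3 | 0.605 | 0.633 | 1.050 |
| 5 | 0.608 | 0.654 | 1.083 |

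If deaths are censored in both arms, the HR stays at 0.600. If half of the TACE deaths are counted at k = 5, it is 0.654 × 64.8/67.3 = 0.630.

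**6. Scale against sampling error.** SE(log HR) ≈ 2/√120 = 0.183. Compared with equal counting, the log shift is ln[(64.8+k)/64.8]: 0.015 at k = 1 and 0.074 at k = 5. That is about 0.08 to 0.41 of one standard error.

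**The case against.** The strongest reply is that the asymmetry is an accident of layout. If standing under the 10.3 heading made a sentence SBRT-only, the general analysis and removal rules there would be SBRT-only too, which nobody intends. Section 8.1 names only two explanations, progression or treatment toxicity, so a TACE patient without progression is already steered toward treatment toxicity. Sections 12.3.1 and 12.4.1 set one labelling process for both arms. This stands to the extent that SBRT-only scope cannot be asserted as fact. It does not remove the point, because 8.1 sets no default and the reader still has to guess.

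A reader might infer four stronger things that the documents do not support:

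- *Liver deaths without progression count under SBRT by rule.* The bullet is about enzyme rises and early signs of injury. It does not mention cause of death, and 17.1 does not cite it. Carrying it over to deaths is an inference.
- *The trial's main result is biased.* The primary analysis counts all deaths. In the secondary analysis the error would run against SBRT, so it could not manufacture a benefit.
- *Serious liver events after TACE would go unseen.* Sections 12.4.4 and 18.2 send all SAEs to the coordinating center within one working day, whatever their relatedness, and 18.2 has a committee review them in real time. Only the IRB route depends on the label.
- *A planned arm comparison of related liver events is distorted.* No such comparison is planned.

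**Conclusion.** The point holds as an unclear attribution rule, not as a demonstrated tilt. The presumption is printed once, under the SBRT heading, with no TACE counterpart and wording that leaves its reach open. Unblinded investigators may therefore label equal liver injuries differently by arm. The exposure is to relatedness labels, to IRB reporting and, conditionally, to one secondary analysis.

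The size in that analysis rests on three assumptions: the rule is read as SBRT-only, it is extended to deaths, and the matching TACE deaths are all called unrelated. The upper figures in the working also need five such deaths per arm. The plan expects low mortality, so a shift near the low end, or none, is more likely. Even the upper figure is under half a standard error. The case for acting is that the correction is nearly free.

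**What to change.** 1. Move the attribution sentence from 10.3 to section 10.0 and name both arms, for example: *In either arm, liver injury in these subjects without documented tumor progression is presumed related to protocol treatment.*
2. Reconcile it with 8.1, so that the imaging work-up and the default attribution read as one procedure. The removal criterion in 10.3 also depends on attribution to treatment, so the sponsor should check that these passages agree. No change to the clinical rule itself is suggested here.
3. In 17.1, state that relatedness of death is judged by this same rule in both arms. Review of deaths by people unaware of the arm would be a further safeguard, but it is not needed to remove the inconsistency.

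The cost is one sentence moved, one clause added and one cross-check with 8.1. The downside is that somewhat more TACE liver events may be labelled related and reported to the IRB.
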